¹ Based on the normal approximation to the binomial distribution. Upper bound capped at 100% and lower bound capped at 0%.

² Injection appointments that result in shows were defined as an injection at visit N occurring during the target window. Baseline visits were excluded as no scheduled date was recorded. Participants who withdrew during the target window were counted as no shows.

³ Missed appointments were defined as any appointment for which no injection occurred among participants who reached the target window prior to study discontinuation.

⁴ No missed dose forms were completed, therefore participant and HIV care provider notification could not be determined.

⁵ Return rate was determined by counting the number of participants receiving an injection at visit N based on the number expected according to the number of participants at the previous visit.

⁶ Eligible participants included consented, declined study participation, not scheduled/lost to follow-up after referral. Eligible participants excluded those not receiving CABENUVA due to lack/change of insurance or cancellation by HCP, not enrolled due to site closure, not attending infusion center, and unknown and was prescribed CABENUVA every other month (before permitted in study) and <18 years of age.

 $^{^{7}}$ Target dates for injections were determined in accordance with the methodology implemented in the PLWHIV outputs. Abbreviations: CI = Confidence interval; HIV = human immunodeficiency virus; IC/ASA = infusion center/ alternate site of administration; IM = intramuscular; N/A = Not available; NE= Not estimable

A Phase 4, Open-label, Single-arm Study to Optimize Implementation of CABENUVA for the Treatment of HIV-1, for Administration in US Community-based Infusion Centers or Alternate Site of Administration

Table 7.2 IC/ASA Metric Reporting - Palmetto

Table 7.3 IC/ASA Metric Reporting - Medix

Table 7.4 IC/ASA Metric Reporting - Infusion Associates

Table 8. Distributional Characteristics of the Feasibility Composite Score

	Number of Clinics ¹	Missing	Mean	SD	Median (Q1, Q3)	Range (Min, Max)	95% Cl (Lower, Upper)	Cronbach's α²
Feasibility Composite Score ³	XX	XX	XX.X	XX	XX (X.X, X.X)	(X.X, X.X)	(X.X,X.X)	X.XX
FIM Score ⁴	XX	XX	XX.X	XX	XX (X.X, X.X)	(X.X, X.X)	(X.X,X.X)	X.XX
Consent Rate	XX	XX	XX.X	XX	XX (X.X, X.X)	(X.X, X.X)	(X.X,X.X)	X.XX
Show Rate	XX	XX	XX.X	XX	XX (X.X, X.X)	(X.X, X.X)	(X.X,X.X)	X.XX
Return Rate	XX	XX	XX.X	XX	XX (X.X, X.X)	(X.X, X.X)	(X.X,X.X)	X.XX

Feasibility composite score includes FIM score, consent rate, show rate, participant notification appointment level, HIV care provider notification, and return rate across the entire study period within each clinic.

Participants are assigned to clinics based on the initial referral.

Participants are assigned to clinics based on the initial referral.

Abbreviations: CI = Confidence interval; FIM = Feasibility of Intervention Measure; SD = Standard deviation

¹ Includes only clinics consenting one or more participants.

 $^{^2}$ Standardized Cronbach's α . For components, Cronbach's alpha if item deleted is presented.

³ Feasibility composite score includes FIM score, consent rate, show rate, and return rate across the entire study period within each clinic. Participant notification appointment level, and HIV care provider notification were excluded as no missed dose forms were completed.

⁴ Based on proportion of PLWHIV endorsing all FIM items at a level of 4 or 5 at any timepoint.

A Phase 4, Open-label, Single-arm Study to Optimize Implementation of CABENUVA for the Treatment of HIV-1, for Administration in US Community-based Infusion Centers or Alternate Site of Administration

Table 9. Implementation Science-Related Protocol Deviations, N=XX

Protocol Deviation	IS-related Protocol Deviations For IC/ASA Staff (N= XX)	
	n(%)	
Total Sample IS-related Protocol Deviations	xx (xx.x)	
Questionnaire missing data	xx (xx.x)	
Questionnaire completed but not required	xx (xx.x)	
Questionnaire completed out of window (early)	xx (xx.x)	
Questionnaire completed out of window (late)	xx (xx.x)	
Duplicate questionnaire completed	xx (xx.x)	
Placeholder, other possible deviation	xx (xx.x)	

Abbreviations: IC/ASA = infusion center/ alternate site of administration

[figure not shown]
Note: Numerators equal the number of IC/ASA staff experiencing respective deviation type, denominators equal the number of IC/ASA staff in analytic dataset

 $^{^{1}}$ Deviations associated with incomplete IS questionnaires are for those initiated but not completed

8 Figures

[figure not shown]
Figure 1. Bar Chart Showing Mean IC/ASA Staff FIM and AIM Responses at Baseline, Month 3, and Month 8

Abbreviations: IC/ASA = Infusion center/ alternate site of administration; FIM = Feasibility of Intervention Measure; AIM = Acceptability of Intervention Measure; BL=Baseline; M3 = Month 3; M8 = Month 8 Error Bars = Standard error

Figure 2. Bar Chart Showing Proportion of IC/ASA Staff Responding "Agree" or "Completely Agree" on All FIM Items at Baseline, Month 3, and Month 8

[figure not shown]
Abbreviations: IC/ASA = Infusion center/alternate site of administration; FIM = Feasibility of Intervention Measure; BL=Baseline; M3 = Month 3; M8 = Month 8

Responses: 4=CCI 5=CCI

For each time point, numerator = number responding '4' or '5', denominator = number completing all 4 items

Error Bars = Standard error

Figure 3. Bar Chart Showing Proportion of IC/ASA Staff Responding "Agree" or "Completely Agree" on All AIM Items at Baseline, Month 3, and Month 8

[figure not shown]
Abbreviations: IC/ASA = Infusion center/alternate site of administration; AIM = Acceptability of Intervention Measure;

BL=Baseline; M3 = Month 3; M8 = Month 8 Responses: 4=CCI , 5=CCI

For each time point, numerator = number responding '4' or '5', denominator = number completing all 4 items $Error\ Bars = Standard\ error$

Figure 4. Bar Chart Showing Change in Proportion of IC/ASA Staff Responding "Agree" or "Completely Agree" on All FIM Items, Baseline to Month 3, Baseline to Month 8, and Month 3 to Month 8

Abbreviations: IC/ASA = Infusion center/alternate site of administration; FIM = Feasibility of Intervention Measure; BL=baseline; M3 = Month 3; M8 = Month 8

[figure not shown]
Responses: 4=CCI 5=CCI

Note: Each bar is limited to those completing all 4 items at both respective timepoints; numerator = number responding '4' or '5', denominator = number completing all 4 items

Error Bars = Standard error

Figure 5. Bar Chart Showing Change in Proportion of IC/ASA Staff Responding "Agree" or "Completely Agree" on All AIM Items, Baseline to Month 3, Baseline to Month 8, and Month 3 to Month 8

Abbreviations: IC/ASA = Infusion center/alternate site of administration; AIM = Acceptability of Intervention Measure; BL=baseline; M3 = Month 3; M8 = Month 8

Responses: 4=CCI 5=CCI

Note: Each bar is limited to those completing all 4 items at both respective timepoints; numerator = number responding '4' or '5', denominator = number completing all 4 items

Error Bars = Standard error

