11. Answering patient questions between visits	XX	n (%)	n (%)	n (%)	n (%)	n (%)	n (%)
12. Managing patients who present to CABENUVA appointments with other care needs that need to be addressed	XX	n (%)	n (%)	n (%)	n (%)	n (%)	n (%)
13. Management of scheduling appointments during correct treatment windows	XX	n (%)	n (%)	n (%)	n (%)	n (%)	n (%)
14. Management of rescheduling appointments during correct treatment windows	XX	n (%)	n (%)	n (%)	n (%)	n (%)	n (%)
15. Management of confirming patient insurance coverage	XX	n (%)	n (%)	n (%)	n (%)	n (%)	n (%)
16. Patient insurance coverage clearing for payment	XX	n (%)	n (%)	n (%)	n (%)	n (%)	n (%)

NOTE: all items are 'select one response'; Table will be sorted from highest to lowest percentage, at baseline, of IC/ASA Staff indicating extremely concerned, followed by moderately concerned, somewhat concerned, slightly concerned, and not at all concerned. The top 5 items in terms of percent indicating extremely concerned at baseline will be **bolded** at all subsequent time points. Tables reporting subsequent time points will be sorted the same as baseline table.

Abbreviation: IC = infusion center; ASA = alternative site of administration; HIV = human immunodeficiency virus

NOTE: Missing = the number of participants who are eligible to complete a survey at the respective timepoint but did not complete respective item; Missing % = the number of participants who were eligible to complete a survey at the respective

timepoint but did NOT complete the respective item / the number of people who were eligible to fill out a survey at the respective timepoint. Cell percentages do not include missing.

Table 1.2.3. IC/ASA Staff Concerns about CABENUVA Administration – Month 8 (N=XX)

Table 1.3.1. IC/ASA Staff Feedback on IC/ASA Administration Blueprint, Month 3 (N=XX)

Question	Number of Participants at Month 3	Response	n (%)
		PowerPoint	n (%)
		Word document	n (%)
1. In which format did you receive the	XX	Both	n (%)
blueprint? ^{1,2}	700	I did not receive the blueprint (skip remaining)	n (%)
		Missing	n (%)
		PowerPoint	n (%)
2. Which format do you prefer for the	VV	Word document	n (%)
blueprint? ^{1,2}	XX	Either format	n (%)
		Missing	n (%)
		Extremely often	n (%)
		Very often	n (%)
2 Have aftern da via viva an mafainta	XX	Somewhat often	n (%)
3. How often do you use or refer to the blueprint?1		Seldom	n (%)
·		I have never used or referred to the blueprint (skip remaining)	n (%)
		Missing	n (%)

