		Extremely useful	n (%)
		Very useful	n (%)
		Somewhat useful	n (%)
4. How useful is the blueprint? ¹	XX	Neutral	n (%)
		Not very useful	n (%)
		Not at all useful	n (%)
		Missing	n (%)
		Strongly agree	n (%)
		Agree	n (%)
5. The blueprint contains the information I need to administer	XX	Neither agree nor disagree	n (%)
CABENUVA at my infusion center. ¹	^^	Disagree	n (%)
		Strongly disagree	n (%)
		Missing	n (%)
		Strongly agree (go to 6a)	n (%)
6. There is information I need for administering CABENUVA in my	XX	Agree (go to 6a)	n (%)
2		Neither agree nor disagree (go to 7)	n (%)

Question	Number of Participants at Month 3	Response	n (%)
infusion center that is missing from		Disagree (go to 7)	n (%)
the blueprint. ¹		Strongly disagree (go to 7)	n (%)
		Missing	n (%)
6a. What do you think is missing from	XX	Open-ended text*	n (%)
the blueprint? ^{1,3,4}	^^	Missing	n (%)
		Extremely positive	n (%)
		Very positive	n (%)
		Somewhat positive	n (%)
7. What is your overall opinion of the	VV	Neutral	n (%)
blueprint? ^{1,5}	XX	Somewhat negative	n (%)
		Very negative	n (%)
		Extremely negative	n (%)
		Missing	n (%)

¹ Select one response

NOTE: Missing = the number of participants who are eligible to complete a survey at the respective timepoint but did not complete respective item; Missing % = the number of participants who were eligible to complete a survey at the respective timepoint but did NOT complete the respective item / the number of people who were eligible to fill out a survey at the respective timepoint. *"Other" responses and open-ended text responses will be presented in an appendix

Cell percentages do not include missing and responses from participants who completed items which violated the prescribed skip pattern were omitted.

Abbreviations: IC = infusion center; ASA = alternative site of administration

Table 1.3.2. IC/ASA Staff Feedback on IC/ASA Administration Blueprint, Month 8

Table 2.1. IC/ASA Staff Responding "Agree" or "Completely Agree" On All FIM Items at Baseline, Month 3, and Month 8: Proportions and Change

	Number completing all 4 FIM items	Number endorsing 4 or 5 on all FIM Items	% endorsing all FIM Items	% Point Change
Baseline ¹	XX	XX	XX%	-
Month 3 ¹	XX	XX	XX%	-
Month 8 ¹	XX	XX	XX%	-
Baseline to Month 32	XX	BL=XX M3=XX	BL=XX%; M3=XX%	XX%
Baseline to Month 82	XX	BL=XX; M8=XX	BL=XX%; M8=XX%	XX%
Month 3 to Month 8 ²	XX	M3=XX; M8=XX	M3=XX%; M8=XX%	XX%

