4c. At home, self-administered by you as two injections in your thigh¹ XXX Somewhat interested n (%) A little interested n (%)			Very interested	n (%)
administered by you as two injections in your thigh¹ XXX Somewhat interested n (%) A little interested n (%)	4c. At home, self-		Moderately interested	n (%)
thigh ¹ A little interested n (%)	administered by you as	XXX	Somewhat interested	n (%)
Not at all interested n (%)			A little interested	n (%)
			Not at all interested	n (%)

			Missing	n (%)	
--	--	--	---------	-------	--

¹ Select one response

Abbreviation: HIV = human immunodeficiency virus; PLWHIV = participants living with human immunodeficiency virus NOTE: Missing = the number of participants who are eligible to complete a survey at the respective timepoint but did not complete respective item; Missing % = the number of participants who were eligible to complete a survey the respective timepoint but did NOT complete the respective item / the number of people who were eligible to fill out a survey at the respective timepoint.

Cell percentages do not include missing and responses from participants who completed items which violated the prescribed skip pattern were omitted*"Other" responses and open-ended text responses will be presented in an appendix

Table 1.2.3. PLWHIV Medication Regimen: Experience, Practices, and Views, Month 8

Table 1.3.1. PLWHIV Views on IC Administration Model, Baseline (N=XX)

Question	Number of Participants at Baseline	Response	n (%)
		Very acceptable	n (%)
		Somewhat acceptable	n (%)
		A little acceptable	n (%)
1. How acceptable is it to you to come to the	VOV.	Neutral	n (%)
infusion center for CABENUVA? ¹	XX	A little unacceptable	n (%)
		Somewhat unacceptable	n (%)
		Very unacceptable	n (%)
		Missing	n (%)
		Convenient location of the infusion center	n (%)
		Ease of parking at the infusion center	n (%)
2. What are the		Convenient hours for the infusion center	n (%)
advantages of going to the infusion center to receive CABENUVA? ^{2,3}	XX	More privacy at the infusion center	n (%)
		I like that people do not know what medication I am there to receive	n (%)
		Reduced stigma	n (%)

² Select all that apply

³ Within each question, response choices will be ordered by percent endorsing, descending, ties will go in order presented to respondents. or items with more than 5 response options, the top 5 selected response options within each item at baseline will be bolded in tables for subsequent timepoints.

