³ Within each question, response choices will be ordered by percent endorsing, descending, and ties will go in order presented to respondents. For items with more than 5 response options, the top 5 selected response options within each item at baseline will be bolded in tables for subsequent timepoints.

the infusion center so far? ¹		Neutral	XX (XX.X%)
		A little unacceptable	XX (XX.X%)
		Somewhat unacceptable	XX (XX.X%)
		Very unacceptable	XX (XX.X%)
		I have not interacted with the infusion center yet.	XX (XX.X%)
		Missing	XX (XX.X%)
		Very acceptable	XX (XX.X%)
		Somewhat acceptable	XX (XX.X%)
		A little acceptable	XX (XX.X%)
2. How acceptable was the process of	N=XX	Neutral	XX (XX.X%)
obtaining or dispensing oral		A little unacceptable	XX (XX.X%)
lead in medication? ¹		Somewhat unacceptable	XX (XX.X%)
medication:		Very unacceptable	XX (XX.X%)
		I was not involved in this process	XX (XX.X%)
		Missing	XX (XX.X%)
		Email	XX (XX.X%)
		Fax	XX (XX.X%)
3. How are you		Phone call	XX (XX.X%)
notified if a patient receives	N=XX	Postal Letter	XX (XX.X%)
CABENUVA on time? ^{2,3}		Secure electronic medical record (EMR) message	XX (XX.X%)
		No communication necessary	XX (XX.X%)
		Missing	XX (XX.X%)

		Email	XX (XX.X%)
		Phone call	XX (XX.X%)
4. How are you notified if a patient		Fax	XX (XX.X%)
misses or receives CABENUVA out of	N=XX	No communication necessary	XX (XX.X%)
window at the infusion center? ^{2,3}		Postal Letter	XX (XX.X%)
		Secure electronic medical record (EMR) message	XX (XX.X%)
		Missing	XX (XX.X%)
		In my clinic, by my healthcare staff	XX (XX.X%)
		Infusion Center	XX (XX.X%)
5. Where do	N=XX	Home-nursing visits	XX (XX.X%)
patients in your care receive		At a pharmacy	XX (XX.X%)
CABENUVA? ^{2,3}		Through a mobile van service	XX (XX.X%)
		Other*	XX (XX.X%)
		Missing	XX (XX.X%)
6. Do you recall seeing or	N=XX	No or not sure (skip all remaining questions)	XX (XX.X%)
completing the		Yes	XX (XX.X%)
plan of treatment (POT)? ¹		Missing	XX (XX.X%)
7. The information		Strongly Agree	XX (XX.X%)
included in the plan of treatment		Agree	XX (XX.X%)
(POT) is comprehensive	N=XX	Occasionally	XX (XX.X%)
enough for the infusion center to		Neither agree nor disagree	XX (XX.X%)
administer		Disagree	XX (XX.X%)

CABENUVA to patients. ¹		Strongly disagree	XX (XX.X%)
'		Missing	XX (XX.X%)
		Strongly Agree	XX (XX.X%)
8. The plan of		Agree	XX (XX.X%)
treatment (POT) has all of the		Occasionally	XX (XX.X%)

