injections at the infusion center?1		Neither acceptable nor unacceptable	n (%)
center :*		Somewhat unacceptable	n (%)

		Very unacceptable	n (%)
		Extremely unacceptable	n (%)
		I don't know/haven't talked to a patient about their experiences.	n (%)
		Missing	n (%)
24		Yes	n (%)
34. Have your patients expressed any concerns about		No	n (%)
stigma at the infusion center?1	N=XX	Missing	n (%)
35. Have your patients		Yes	n (%)
expressed any concerns about	N=XX	No	n (%)
privacy at the infusion center?1		Missing	n (%)
36. Do you have any other thoughts or comments about		Open-ended text*	-
your experiences that you'd like to share? Please write in your response below.	N=XX	Missing	n (%)

 $^{^{1}}$ Select one response

Abbreviations: AE = adverse event; ART = antiretroviral therapy; HIV = human immunodeficiency virus; POT = plan of treatment NOTE: Missing = the number of participants who are eligible to complete a survey at the respective timepoint but did not complete respective item; Missing % = the number of participants who were eligible to complete a survey at the respective timepoint but did NOT complete the respective item / the number of people who were eligible to fill out a survey at the respective timepoint.

Cell percentages do not include missing

Table 8.2.2. Expert Panel, Assessment of CABENUVA Administration Moving to Infusion Center, HIV Care Providers – Month 6, (N= XX)

Question	Number of Participants at Month 6	Response	n (%)
		Yes (Go Q9a and Q9b.)	n (%)
9. Have you submitted a referral to the infusion center?	N=XX	No (Go to Q9c.)	n (%)
referrance the imasion center.		Missing	n (%)
	N=XX	Extremely acceptable	n (%)
		Very acceptable	n (%)
		Somewhat acceptable	n (%)
9a. If yes, how acceptable has the referral process been? ^{1,2}		Neither acceptable nor unacceptable	n (%)
the reterral process seem.		Somewhat unacceptable	n (%)
		Very unacceptable	n (%)
		Extremely unacceptable	n (%)

 $^{^{2}}$ Select all that apply

³ Within each question, where appropriate, response choices will be ordered by percent endorsing, descending, and ties will go in order presented to respondents. For items with more than 5 response options, the top 5 selected response options within each item at baseline will be bolded in tables for subsequent timepoints

^{*&}quot;Other" responses and open-ended text responses will be presented in an appendix

Question	Number of Participants at Month 6	Response	n (%)
		Missing	n (%)

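### Respondents correctly routed past a conditional questionnaire item are counted as Missing, because Missing is based on eligibility for the survey and not for the item

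*SAP*

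**What the plan says.** **Definition.** The note under IC/ASA Staff SAP Table 1.3.1 (blueprint feedback, Month 3) reads "Missing = the number of participants who are eligible to complete a survey at the respective timepoint but did not complete respective item". The denominator of Missing % is "the number of people who were eligible to fill out a survey at the respective timepoint". Both parts rest on eligibility for the survey, and neither requires that the item was put to the respondent.

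**Routing in the same tables.**
- Staff Table 1.3.1, item 1: "I did not receive the blueprint (skip remaining". Item 3: "I have never used or referred to the blueprint (skip remaining". Item 4 asks how useful the blueprint is. Item 6a goes only to those who agreed at item 6, yet it has its own Missing row.
- Provider SAP Table 1.2.2 (Month 4) and Table 1.2.3 (Month 8), item 6, recall of the plan of treatment (POT): "No or not sure (skip all remaining questions". The POT questions follow.
- Participant SAP Table 1.2.2, item 1: those with no concerns go straight to question 3.
- Expert Panel Table 8.2.1: items 9a and 9b are for members who have submitted a referral, and item 9c is for those who have not.

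**The only clause on skips.** Under staff Table 1.3.1 and some other tables: "Cell percentages do not include missing and responses from participants who completed items which violated the prescribed skip pattern were omitted". The notes under provider Tables 1.2.2 and 1.2.3 have no such clause.

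**Deviations.** Section 2.4 of both the staff and the participant SAP treats a questionnaire as deviating if any item is missing and the person has not dropped out. By-design skips are not mentioned.

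**The concern.** A blank on a conditional item can mean two things: the respondent was asked and did not answer, or was correctly not asked. Only the first is missing data. The stated rule adds the two together and divides by a base that includes people to whom the item did not apply. The printed Missing n and % are then wrong as measures of non-response.

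This reaches items that serve secondary endpoints in Protocol Section 3, namely usefulness of the blueprint to IC/ASA staff and of the POT to providers. It can also make a favourable result look like poor data: the more participants report no concerns, the higher the Missing % on the list of concerns. If the same reading is carried into Section 2.4, people who completed their forms exactly as instructed are listed with a deviation.

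**Working it through.** There is no planned figure to reproduce. The check sets the rule against the routing.

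**Formulas.** Let E be those eligible for the survey, S those routed past the item, and M those routed to it who did not answer.
- Missing % as written = (S + M) / E.
- Missing % among those routed to the item = M / (E − S).
- If M = 0, the first equals S / E and the second is 0. So the first can never be below the share routed past.

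**A case that needs no assumed numbers.** In Expert Panel Table 8.2.1, items 9a and 9c apply to complementary groups. With everyone responding and the routing followed, those who have not submitted a referral are Missing on 9a, and those who have submitted one are Missing on 9c. The two Missing percentages add to 100% with no non-response at all.

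**Illustration 1 (assumed: 60 eligible staff, all forms complete, 10 non-receivers, 15 never-users).**
- Item 2: S = 10, so Missing % = 10/60 = 16.7%; true non-response is 0%.
- Item 4: S = 10 + 15 = 25, so Missing % = 25/60 = 41.7%; among those routed to it, 0/35 = 0%.

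**Illustration 2 (sizes from Protocol Section 6.1; skip shares and 5% non-response among those asked are assumed; counts rounded).** Staff: about 5 at each of about 35 sites, 5 × 35 = 175. Providers: about 20.

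| Item | Routed past | Not answered | As written | Among those routed to it |
|---|---|---|---|---|
| Staff item 4, 20% skip | 35 | 7 | 42/175 = 24.0% | 7/140 = 5.0% |
| Staff item 4, 40% skip | 70 | 5 | 75/175 = 42.9% | 5/105 = 4.8% |
| Provider POT items 7 and 8, 40% skip | 8 | 1 | 9/20 = 45.0% | 1/12 = 8.3% |

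Over assumed skip shares of 20% to 60% with no true non-response, Missing % is 20% to 60% as written and 0% on the routed base.

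**Does the skip clause cure it?** No. It removes answers given against the routing. A correct skip leaves no answer to remove and still meets the definition of Missing.

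**Scope.** The rule and routed items occur together in staff Tables 1.1.2 and 1.3.1; participant Tables 1.2.1, 1.2.2 and 1.3.2; provider Tables 1.2.2 and 1.2.3; and the Month 3 and Month 6 Expert Panel tables in the 8 series. Staff Table 1.3.2 (Month 8) is given by title only, and I assume it follows 1.3.1. Provider Tables 1, 1.3.1 and 1.4.1 to 1.4.3 define Missing differently, by completion of any part of a survey at any time, but hold no skip-routed items. POT item 9 has no Missing row.

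**The case against.** The strongest reply is that little information is lost. Three inferences are tempting, and the documents do not support them.

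- *Non-use is hidden or reported only as poor data quality.* It is not. Non-receipt and non-use of the blueprint have their own n (%) rows at items 1 and 3 of staff Table 1.3.1, and non-recall of the POT has one at item 6 of provider Tables 1.2.2 and 1.2.3.
- *True non-response cannot be separated from a correct skip.* It largely can, by subtraction. In the first illustration, item 4 shows 25 Missing, items 1 and 3 show 10 and 15, and 25 − 10 − 15 = 0.
- *The usefulness percentages are distorted.* They are not, because Missing is already outside their denominator. If 20 of the 35 users in the first illustration rated the blueprint extremely or very useful, the table would give 20/35 = 57%. The figure 20/60 = 33% answers a different question and counts people who were never asked as not finding it useful.

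It is also fair that several conditional items carry footnotes saying to whom they were administered, that each question has its own cell for the number of participants, and that a programmer might restrict Missing sensibly in practice.

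All of this limits the consequence. It does not make the stated Missing n and % right: the notes define both explicitly on the survey base, and the administered-to footnotes are not carried into that definition.

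**Conclusion.** The point holds for the Missing n and Missing % rows of conditional items in the tables listed. Followed as written, the rule counts every correct skip as missing, so Missing % is at least the share routed past the item. The size in this study is unknown because the documents give no skip rates. The 42% against 0% rests wholly on assumed numbers and shows the mechanism only.

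The effect on the deviation tables is possible rather than certain. Section 2.4 of the staff and participant SAPs does not say whether a by-design skip is a missing item, and nothing there excludes it. In the first illustration, a literal reading would give at least 25 of 60 staff a missing-data deviation although every form was complete.

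Percentages among those who answered stand, and the gate items already report non-receipt, non-use and non-recall. The primary endpoint is untouched, because the FIM items are asked of everyone. This is a reporting rule to correct before the tables are produced, not a threat to the study's conclusions.

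**What to change.** - For conditional items, define Missing as routed to the item but not answered, and take Missing % over those routed to it.
- Add a row *Not applicable (skipped by design)* with n and % to every question that a skip instruction can bypass.
- State how someone who left the gate item blank, or returned no form, is counted, since their routing is unknown.
- In Section 2.4 of the staff and participant SAPs, exempt by-design skips from the missing-data deviation.
- Settle the routing of staff Table 1.3.1 item 7 first. Item 6 sends those who strongly disagree on to item 7, but footnote 5 names only the neutral and disagree answers, so who was due to answer is not yet defined.

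Reporting usefulness among all respondents as well as among users is optional; it is not a correction.

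The cost is a revised footnote, one extra row per conditional item and a routing flag derived from answers already collected.
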